### **5.2.2 Seizure Frequency**

Seizure frequency will be collected in subject diaries and all seizures reported in the diaries will also be reported as AEs on the adverse events eCRF page.

For the purpose of summarizing seizures, the more granulated information from AE pages will be used. Each AE with preferred term including the word "seizure" will be considered a seizure for the purpose of this analysis.

For each subject the number of seizures per the following 3-month intervals will be calculated:

1. Pre-treatment,
2. Baseline to month 3 (study days 1 to 90; both inclusive),
3. 4 to 6 months (study days 91 to 180; both inclusive),
4. 7 to 9 months (study days 181 to 270; both inclusive),
5. 10 to 12 months (study days 271 to 360; both inclusive),
6. 13 to 15 months (study days 361 to 450; both inclusive),
7. 16 to 18 months (study days 451 to 540; both inclusive),
8. After 18 months (study day 541 and onwards),
9. Entire study duration (all previous combined).

Qualifying AE start days will be compared with the study days above to determine in which time interval the seizure occurred. For study day 1, treatment start time and AE start time will additionally be compared. In case of missing or partial AE start dates, imputation rules provided in section [8.1](#) will be used for determining the interval in which the seizure occurred.

Summary statistics of seizure counts for all subjects in the Efficacy Population will be provided by time interval. Individual seizure counts by time interval will be provided in a listing.

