F Since last Local Health Center/ Subject's Home visit.

G Chemistry laboratory parameters include HbA1c, creatinine, total bilirubin (direct and indirect if values were above normal ranges), alkaline phosphatase, aspartate aminotransferase, alanine aminotransferase, gamma glutamyl transpeptidase, creatine kinase, sodium, potassium, cholesterol, and triglycerides. Hematology laboratory parameters include hemoglobin, hematocrit, erythrocytes, thrombocytes, and white blood cell count with differential (for an absolute neutrophil count, lymphocyte count and monocyte count). Dipstick urinalysis includes glucose, nitrate, hemoglobin, leukocytes, protein, pH, ketones, and specific gravity.

H All subjects will be assayed for anti-hepatitis C antibody, hepatitis B surface antigen, and human immunodeficiency virus.

I Assessment will be done either before or > 24 hours after sedation. All domains are administered at baseline. If video interview is not possible for technical reasons, patients will be assessed at the NIH by a UBDRS trained rater. In cases of any event precluding safe travel by participants to NIH, the assessment will be performed remotely according to instructions delivered by URMC

J Assessment will be done either before or > 24 hours after sedation. The Communication, Daily Living Skills, Socialization and Motor Skills domains are assessed.

K Subjects who cannot cooperate with the MRI study, ophthalmology exam, or lumbar puncture procedure may be sedated. Baseline OCT will be obtained in all study participants. In those participants with no light perception vision, dense cataracts, or other ophthalmologic findings that produce significant artifacts in the OCT images, OCT imaging will not be repeated.

L A seizure diary will be completed on a daily basis, beginning at screening. The baseline seizure frequency will be calculated based on data collected from screening to first dose of study drug.

**Table 1-3 Miglustat Dose-titration and Pharmacokinetic Sampling Period – Local Health Center or Subject’s Home (Weeks 1 Through 9)**

	Day 1 – Week 1 (Within 42 days of screening)	Dose-titration Period							
		Day 8±2 Week 2	Day 15±2 Week 3	Day 22±2 Week 4	Day 29±2 Week 5	Day 36±2 Week 6	Day 43±2 Week 7	Day 50±2 Week 8	Day 57±2 Week 9
General Assessments									
Abbreviated physical examination A	X				X				X
Vital signs B	X	X	X	X	X	X	X	X	X
Weight	X	X	X	X	X	X	X	X	X
Concomitant medications	X	X	X	X	X	X	X	X	X

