### 3 STUDY OBJECTIVES AND ENDPOINTS

Objectives	Endpoints
Primary	

 
To assess the safety and tolerability of the Batten-1 treatment regimen over the study period
 
	
 
Incidence of treatment-emergent adverse events (TEAEs) and serious adverse events (SAEs); changes in baseline in clinical laboratory tests (hematology, chemistry, and urinalysis), 12-lead electrocardiogram (ECG) findings, slit lamp evaluation, vital signs (heart rate and systolic and diastolic blood pressure) as well as physical and neurological examinations
 

Secondary	

 
To assess the pharmacokinetics (PK) of miglustat in subjects with CLN3 disease
 
	
 
Week 1 (first dosing: Maximum plasma concentration (Cmax), Time to Cmax (Tmax), area under the concentration-time curve calculated to the last observable concentration at time t (AUC 0-t), area under the concentration-time curve extrapolated to infinity (AUC0-<math>\infty</math>), elimination half-life (T1/2))
 
Week 9 Repeated dose (steady state): Cmin, Cmax, Tmax, AUC 0-8hr
 

 
To assess the effect of the Batten-1 treatment regimen on the longitudinal progression of clinical signs or symptoms of CLN3 disease.
 
	
 
Unified Batten Disease Rating Scale (UBDRS)
 
Seizure frequency (diaries)
 
Vineland Adaptive Behavior Scales, Version 3 (Communication, Daily Living Skills, Socialization, and Motor Skills domains)
 
Ophthalmic assessments including visual acuity, visual fields (if applicable), and optical coherence tomography (OCT)
 
Magnetic resonance imaging (MRI)
 

Exploratory	

 
To assess potential biomarkers of CLN3
 
	
 
Measure biomarkers in cerebrospinal fluid (CSF), blood and urine.
 

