#### 7.3.2 Seizure Frequency

Subjects will receive a seizure diary to be completed at screening. Diaries will be collected during the Local Health Center / Subject's Home visits and will be shipped to TCH. The baseline seizure frequency will be calculated based on data collected from screening to first dose of study drug. The report template is provided in [Section 13.3](#).

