### 13.3 Appendix 3: Seizure Diary

Protocol # \_\_\_\_\_

Subject ID: \_\_\_\_\_

Page 1 of 3

1. Take this diary home and use it every day to keep track of your seizures.
2. The staff will review your seizures with you and each seizure type will be assigned a special code.
3. If you have a seizure, record the number of seizures and the type of seizure (using the assigned code below) on the diary.
4. If you do not have any seizures on that day, mark the 'no seizure' box.
5. Bring the seizure diary with you to your next appointment.

Seizure Code	Description given by patient/caregiver

Example:

	Enter the date here
	If you had any seizures that day, write down the number of seizures you had next to the seizure type. In this example, the subject had two A seizures.
 No Seizures Today	Mark the no seizure box if you did not have any seizures that day.

Protocol # \_\_\_\_\_

Subject ID: \_\_\_\_\_

Page 2 of 3

Month: \_\_\_\_\_ Year: \_\_\_\_\_

SUNDAY	MONDAY	TUESDAY	WEDNESDAY	THURSDAY	FRIDAY	SATURDAY
 No Seizures						
 No Seizures						
 No Seizures						
 No Seizures						
 No Seizures						
 No Seizures						
 No Seizures						

Who is completing the seizure diary? (check all that apply)  Patient  Caregiver

Comments: \_\_\_\_\_

Protocol # \_\_\_\_\_

Subject ID: \_\_\_\_\_

Page 3 of 3

Month: \_\_\_\_\_ Year: \_\_\_\_\_

SUNDAY	MONDAY	TUESDAY	WEDNESDAY	THURSDAY	FRIDAY	SATURDAY
 No Seizures						
 No Seizures						
 No Seizures						
 No Seizures						
 No Seizures						
 No Seizures						
 No Seizures						

Who is completing the seizure diary? (check all that apply)  Patient  Caregiver

Comments:

---

---

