### 1.1 Changes to the Planned Analyses

The following changes from the protocol were made in this SAP:

1. Adverse Event summaries are presented by system organ class (SOC), high level group term (HLGT) and preferred term (PT) as per Sponsor request, instead of presenting by SOC and PT. HLTG is added to provide more information.
2. According to the protocol, Medical Dictionary for Regulatory Activities (MedDRA; dictionary Version 21.1) and World Health Organization (WHO) Drug Dictionary Version SEP 2018 B3 GLOBAL will be used for coding of adverse events, medical history and medications. In practice, the most recent versions of MedDRA and WHODD available ahead of database lock will be used for coding.

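### Seizure frequency is a daily-diary endpoint, but the SAP counts it from AE records as raw interval totals, with no check that diary and AE records agree

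*SAP*

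**What the plan says.** Protocol section 3 and SAP Table 1 both list seizure frequency as a secondary endpoint and name the diaries as its source. Protocol Table 1-2, footnote L: "A seizure diary will be completed on a daily basis, beginning at screening". The diary form (Protocol Appendix 3) tells the family: "If you have a seizure, record the number of seizures and the type of seizure (using the assigned code below) on the diary". A separate box is ticked on days without a seizure. Protocol 7.3.2, the diary section, adds: "The baseline seizure frequency will be calculated based on data collected from screening to first dose of study drug".

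SAP 5.2.2 takes another route. It first states that every seizure in the diary is also entered on the AE page. It then says that "the more granulated information from AE pages will be used" for the summary, with this rule: "Each AE with preferred term including the word 'seizure' will be considered a seizure for the purpose of this analysis". Each such AE is placed by its start day into one of these intervals: pre-treatment (no day limits given), six 90-day intervals from Day 1 to Day 540, everything from Day 541 on, and the whole study. Summary statistics of the counts are tabulated by interval, and individual counts are listed. Missing or partial start dates follow SAP 8.1.

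SAP 1.1, introduced by "The following changes from the protocol were made in this SAP", lists two items: the extra MedDRA level in AE tables and the dictionary versions. The seizure data source is not among them.

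**The concern.** The diary holds what a frequency needs: a number per day, by type, and a positive mark for days without seizures. The SAP gives no reason why AE pages are finer for counting. An AE record is designed to describe an event, not to tally episodes, and it reaches this analysis only after coding and a word search. The AE count equals the diary count only if every diary seizure becomes an AE, each AE record is one seizure, every coded term contains the word, and every start date is known well enough to place it.

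The second issue is the summary measure. A count is not a frequency unless the observation periods are equal, and here they are not.

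At stake is a secondary efficacy result in about six subjects with no control arm, where the reader's only comparison is each interval against pre-treatment.

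**Working it through.** No figure in the plan can be reproduced: the sample size rests on availability, and efficacy is descriptive. The check sets the rules side by side and then works through two short calculations.

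**1. Does the AE route carry the diary count?**

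- *Entry as AE.* SAP 5.2.2 says all diary seizures are entered. The protocol's diary sections (7.3.2, Table 1-2 footnote L, Appendix 3) carry no matching instruction to sites.
- *One record per seizure.* Protocol 7.1.1.2 asks that an event that stops and restarts be reported each time. That supports separate records. It does not say how a day with several seizures is entered, and the diary form's own worked example is a day with two.
- *Matching term.* SAP 5.2.2 gives a word search but no term list and no medical review. Protocol 7.1.1.2 asks for the diagnosis rather than signs or symptoms where one can be established, so the recorded term need not name the seizure. The dictionary version is whichever is latest before lock (SAP 1.1).
- *Date.* Under SAP 8.1 a start date that is wholly unknown is set to study drug start. The same holds if only the year is known and it is the start year, or if month and year match those of first dose. An earlier known end date overrides this. SAP 5.1.1 treats a Day 1 event of unknown time as treatment-emergent. By that rule a pre-treatment seizure with such a date would fall in Days 1–90. Diary entries are kept by calendar day.
- *Reconciliation.* SAP 5.2.2 plans none.

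**2. How a miscount would scale (illustration only)**

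Counted / true = c × f / m, where c is the share of diary seizures entered as AEs, f the share of those whose term contains the word, and m the seizures per AE record. The documents give none of these. Assume 30 true seizures in 90 days:

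| c | f | m | Counted | Change |
|---|---|---|---|---|
| 1 | 1 | 1 | 30 × 1 = 30 | none |
| 1 | 0.9 | 1 | 30 × 0.9 = 27 | −10% |
| 1 | 0.7 | 1 | 30 × 0.7 = 21 | −30% |
| 1 | 1 | 2 | 30 / 2 = 15 | −50% |
| 0.9 | 0.9 | 2 | 30 × 0.405 = 12.2 | −60% |

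The first row is what the SAP takes for granted. AE records with no diary entry would push the other way. The table shows sensitivity; it does not estimate an error.

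**3. Unequal intervals (follows from the documents' own day limits)**

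With a constant rate r per day, the expected count is r × days, so the ratio of two intervals does not depend on r.

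- Pre-treatment is nominally Days −42 to −1 (Protocol Table 1-2), 42 days. First on-treatment interval: 90 days. Ratio 90/42 = 2.14.
- The synopsis puts screening to first dose at about 4 weeks, 28 days. Ratio 90/28 = 3.21.
- Table 1-2 footnote B allows, when travel is unsafe, up to 3 months between the two inclusion visits and 1 month to first dose. With 30-day months that is 120 days. Ratio 90/120 = 0.75.
- The last interval is open-ended. Treatment may last up to 116 weeks: 116 × 7 = 812 days, and 812 − 540 = 272 days. Ratio 272/90 = 3.02.

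At an assumed 10 seizures per 30 days, expected counts are 9.3 in 28 days, 14.0 in 42, 30.0 in 90 and 90.7 in 272, with no change in the subject's condition.

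**The case against.** The AE page is not an unrelated source. The SAP says it carries the diary seizures forward, and the protocol wants recurrences reported. AE records also hold start time, severity and outcome, which may be what the SAP means by finer detail. The SAP is based on a CRF version that is not among the documents, so the AE page may already hold one row per seizure. The UBDRS frequency items nearly all carry the word seizure in their titles, so most events may code to a matching term. With six subjects, the AE listing and the individual seizure counts let a reader spot omissions; medians and ranges accompany means; and UBDRS items 23–34 assess seizures separately. Protocol 8.9 leaves detail to the SAP, and 5.2.2 states its source openly.

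Much of this stands, and it rules out three stronger readings that a reader might infer:

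- *That seizures will be undercounted by a known share, or that multi-seizure days will be halved.* No text says that seizures are merged into one record, and which preferred terms lack the word depends on a dictionary that is not supplied.
- *That AE recording differs before and after first dose.* AEs are recorded from consent by the same route throughout. The one date-related exception is the imputation rule.
- *That using AE pages is what makes the counts non-comparable.* Diary counts summarised as raw totals would have the same fault. AE pages alone do lack a record of which days were observed.

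The objection does not answer the remaining points. Reporting each recurrence is not a rule of one record per seizure. A statement that entry will happen is not a check that it did. Listings let a reader notice a discrepancy only if diary counts are shown beside AE counts, and 5.2.2 does not plan that.

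**Conclusion.** The point holds as a gap between the defined endpoint and its planned derivation, and should be closed before database lock. The source and counting rule differ from the endpoint's definition, agreement between the two sources is assumed without verification, and the change is not declared in SAP 1.1.

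The direction and size of any miscount cannot be derived from the documents. It is zero if entry, coding, dating and one-record-per-seizure all hold and no non-diary record matches. Undercounting is the likelier direction if they do not.

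The interval problem can be sized. At the nominal 42-day pre-treatment window, an unchanged rate yields a count 2.1 times higher in the first 90 days on treatment. The factor runs from 3.2 at 28 days to 0.75 at 120 days, so it also varies between subjects. This assumes a constant rate and full observation of each interval.

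The consequence is limited: a descriptive secondary endpoint with no test. It would not be right to infer that the trial's seizure results are wrong; the plan as written cannot show that they are right.

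**What to change.** In SAP 5.2.2:

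1. Derive seizure counts from the diary by day and type.
2. Report every interval, including pre-treatment and the period after Day 540, as seizures divided by diary days observed, and show the number of observed days. For pre-treatment this restores the baseline frequency described in Protocol 7.3.2.
3. Reconcile diary and AE records subject by subject before lock and list the differences.

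If AE records remain the source:

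1. Select them by a medically reviewed list of preferred terms fixed before database lock.
2. Check the number of episodes per record against the diary, and take dates from the diary where the AE start is incomplete.
3. Still report rates per observed time.
4. List the change of source, with its reason, in SAP 1.1.

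The cost is SAP wording, some programming, and possibly entry of diary pages already collected for six subjects. No new patient procedure is needed.

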**Number of Participants and Duration of Participation:**

Approximately 6 subjects are expected to enroll in the study. Subject participation will be up to 120 weeks (Screening to first dosing approximately 4 weeks, treatment duration up to 116 weeks for the longest treatment duration). Subjects who withdraw or are withdrawn from the study during the titration period may be replaced. The total study duration will be determined based on the early access program actual start for the last patient that will take place within 116 weeks of treatment.

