	Visit 1 Assessments at TCH (Screening and Baseline Safety)	Screening confirmation by TCH A (Phone Visit)	Visit 2 Assessments at NIH CC B and final enrollment (Baseline Efficacy Assessments)	Treatment start Local Health Center/ Subject's Home	Visit 3 NIH CC B	Visit 4 NIH CC B	Visit 5 NIH CC B	Visit 6 Early termination TCH B
				Day 1 Week 1 Up to 14 days between V2 and first dose	Week 26 ( $\pm$ 1 month)	Week 52 ( $\pm$ 1 month)	Week 78 ( $\pm$ 1 month)	Early Access Program start
Days -42 to -1								
MRI K			X		X			
Seizure diary dispensation L	X							
Blood for biomarkers			X		X	X		
Spot urine for biomarkers			X		X			
Lumbar puncture for CSF collection (biomarkers) K			X		X			

A After TCH PI determination of subject eligibility, study staff will inform the subject and will schedule NIH CC baseline visit.

B In cases of any event precluding safe travel by participants to NIH (i) for inclusion visit: beyond 1.5 months, the safety labs will be repeated at NIH. However, the total duration between the 2 inclusion visits should not exceed 3 months. Time between NIH visit and first drug administration should be also maintained within a reasonable timeframe (1 month). (ii) during the course of the study: evaluations will be performed (1) at the Local Health Center / Subject's Home for: labs, ECG (if feasible), physical exam, vital signs, weight, adverse events, or (2) via remote methods for : history, UBDRS, Vineland-3, adverse events, concomitant meds, seizure diary or (3) could be deferred (+/- 1 month) for: neurological exam, ophthalmology exam, MRI, lumbar puncture.

C Vital signs include systolic and diastolic blood pressure [sitting for 5 minutes] and pulse rate.

D A standardized neurological exam will be performed by a pediatric neurologist or qualified individual. The neurological exam will take into account potential visual impairment. The evaluation will include, but is not limited to mental status, cranial nerves, motor function, and sensory and cerebellar functions.

E The subject must be in supine position in a rested and calm state for at least 5 minutes before ECG assessment is conducted. Electrocardiograms should be performed in a standardized method, in triplicate, and approximately 30 seconds apart, prior to blood draws or other invasive procedures. Each ECG must include the following measurements: QRS, QT, QTc, RR, and PR intervals.

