#### *7.1.1.2 Recording Adverse Events*

**Period: Subject Screening to the First Administration of Study Drug:** Non-treatment emergent AEs will be recorded from the time when the subject is screened into the study (date of signature of the informed consent) until first administration of study drug.

**Period: First Administration of Study Drug to Subject's Last Study Visit:** Thereafter all AEs are TEAEs (see Definitions, [Section 7.1.1.1](#)) and will be recorded until the end of study visit has been performed.

**Period After Last Study Visit:** Any SAE occurring after the subject's last study visit that the investigator becomes aware of but considered to be related to the study drug will be reported to the sponsor.

If an AE (serious or not) started during the study but did not end before the final follow-up visit, the investigator should make a reasonable effort to establish the outcome and the end date. If this is not possible, the outcome recorded at the final follow-up visit will be assumed to be the final outcome.

If an event stops and later restarts, all the occurrences must be reported. Adverse events assessed as related to study medication by the investigator and all SAEs must be followed up until resolution.

Signs/symptoms should be documented if a definite diagnosis cannot be established. The investigator should attempt to establish a diagnosis of the event based on signs, symptoms and/or other clinical information. In such cases, the diagnosis should be documented as the AE and/or SAE and not the individual signs/symptoms. If a diagnosis is accompanied by unusual symptoms, the diagnosis itself and the symptoms have to be reported separately.

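### Seizure frequency is tabulated as raw counts over windows of unequal length, so with the planned 28–42 day screening an unchanged seizure rate would appear as a 2.1- to 3.2-fold rise after treatment starts

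*SAP*

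**What the plan says.** The protocol names seizure frequency from diaries as a secondary endpoint. Footnote L to Table 1-2 (Section 1.3) defines the baseline: "The baseline seizure frequency will be calculated based on data collected from screening to first dose of study drug". Protocol 8.5 lists seizure frequency among the baseline disease characteristics to be summarised.

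SAP 5.2.2 takes seizures from the adverse event pages and states: "For each subject the number of seizures per the following 3-month intervals will be calculated". Nine rows follow:

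- Row 1 is pre-treatment, with no length stated.
- Rows 2 to 7 cover study days 1–90, 91–180 and so on to 451–540.
- Row 8 is "After 18 months (study day 541 and onwards".
- Row 9 is "Entire study duration (all previous combined".

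The reported quantity is the count: "Summary statistics of seizure counts for all subjects in the Efficacy Population will be provided by time interval". Neither SAP 5.2.2 nor the general rules in SAP 5.12 give a rate, a days-observed denominator, or a rule for a window that a subject did not complete. SAP 5.7 leaves baseline seizure frequency out of the baseline characteristics, and SAP 1.1 does not list this among the changes from the protocol.

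**The concern.** Counts can be compared only over equal observation time. Rows 1, 8 and 9 are not three-month windows, although the lead-in sentence says they are.

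The row that matters most is the pre-treatment one, because it is the only diary- or event-based baseline the SAP reports. It stands directly above the first 90-day treatment row. A reader comparing the two would mainly see the difference in window length. On the planned schedule that looks like worsening on drug; with travel delays it can look like no change or a fall. Conversely, equal counts in the two rows could hide a real reduction.

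The last row and the whole-study row also depend on when each subject moved to the early access program. The summary table shows no days observed, so its reader cannot correct for any of this.

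**Working it through.** **Inputs**

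- *Start of the pre-treatment window.* Protocol 7.1.1.2 says: "Non-treatment emergent AEs will be recorded from the time when the subject is screened into the study". Collection of these events ends at first dose. No earlier seizures can enter the count.
- *Planned pre-treatment length.* The protocol synopsis gives "Screening to first dosing approximately 4 weeks, treatment duration up to 116 weeks for the longest treatment duration", so about 28 days. Its total of 120 weeks agrees: 4 + 116 = 120. Tables 1-2 and 1-3 allow up to 42 days.
- *Travel exception.* Footnote B to Table 1-2 says "the total duration between the 2 inclusion visits should not exceed 3 months", and allows about one further month to first dose. Taking these as 91 + 30 days gives about 121 days.
- *Rows 2 to 7.* Each is end − start + 1 = 90 days, for example 180 − 91 + 1 = 90.

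**Pre-treatment row against days 1–90**

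At a constant seizure rate r, the expected counts are r × D before treatment and r × 90 in the first treatment window. The ratio is 90/D, whatever r is.

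| Pre-treatment days D | 90/D | Apparent change |
|---|---|---|
| 28 | 3.21 | +221% |
| 42 | 2.14 | +114% |
| 91 | 0.99 | −1% |
| 121 | 0.74 | −26% |

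Read the other way, equal counts in the two rows would mean a true rate reduction of 1 − 42/90 = 53% at 42 days, or 1 − 28/90 = 69% at 28 days.

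**Last row**

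116 weeks × 7 = day 812, and 812 − 541 + 1 = 272 days. 272/90 = 3.02 times a 90-day window. At the other extreme, the protocol's numbering (Week 9 = Day 57) puts Week 78 at days 540–546, so a subject who switches soon after that visit contributes only a few days.

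**Six subjects, unchanged rates**

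The documents give no seizure rate, so a range is assumed. The simulation used 40,000 trials of six subjects. Subject rates were gamma-distributed (shape 1), counts were Poisson, and each subject's rate was the same before and after first dose. Entries are the share of trials in which the days 1–90 summary exceeded the pre-treatment one.

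| Assumed mean rate | Mean count, D 28–42 | Median count, D 28–42 | Mean rate per day, D 28–42 | Mean count, D 28–121 |
|---|---|---|---|---|
| 1 per 7 days | >99% | 98% | 51% | 77% |
| 1 per 30 days | 97% | 86% | 51% | 65% |
| 1 per 90 days | 84% | 58% | 52% | 56% |
| 1 per 180 days | 72% | 30% | 52% | 50% |

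The median count often ties at low rates, which is why its figures drop.

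**The case against.** The strongest reply is that the SAP plans no pre/post contrast for seizures. Where it wants change from baseline, as for the UBDRS and intraocular pressure, it says so. Efficacy is descriptive, the six windows covering days 1–540 are equal, and UBDRS items 23–34 give a separate seizure measure at baseline. Individual counts are listed, so with six subjects a careful reader can look at each one. All of this is true, and it limits the harm to how a table is read. It does not remove the harm. In a six-subject, single-arm study without tests, the descriptive table is the result, and the rows that are equal contain no baseline.

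The second reply is that the direction is not fixed. SAP 6 shows that all six subjects had already completed titration, so the real pre-treatment lengths are settled, but the documents do not give them. This stands: the 2.1- to 3.2-fold figure applies to screening as planned, and the sign can reverse under the travel exception.

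The third reply is that a rate is not a complete cure. Short windows produce more zeros, so the median rate still leans upward at low seizure rates. With an unchanged rate of 1 per 90 days it rises in 52% of simulated trials and falls in 18%. That stands too, but the median count is worse, at 58% up against 6% down. A last window of a few days also gives an unstable rate: one seizure in 3 days becomes 28/3 = 9.3 per 28 days.

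Finally, SAP 5.7 omits other baseline items that protocol 8.5 lists, so the seizure omission is part of a wider gap. That is correct, and it does not excuse this one.

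**Conclusion.** The concern holds and should be fixed. Following the SAP as written gives a distorted baseline row for an endpoint that the protocol defines as a frequency with its own baseline frequency. On the planned 28–42 day screening, an unchanged rate has an expected count ratio of 2.14 to 3.21; at about 121 days the ratio is 0.74. The last row can represent anything from a few days to 272 days, and the whole-study row mixes pre-treatment and on-treatment seizures.

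The ratios assume a constant rate, full observation and complete event capture. The percentages also rest on the assumed seizure rates and the gamma–Poisson model. Rows 2 to 7 remain comparable with one another for subjects observed throughout. The primary safety objective is not affected.

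**What to change.** In SAP 5.2.2:

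- Drop the description of all nine windows as three-month intervals.
- For each subject and window, report seizures per 28 days = 28 × (seizures starting in the window) ÷ (days observed in the window).
- Define pre-treatment days observed as running from the screening informed consent to first dose. Truncate later windows at last contact, for which the End of Study date can serve. Treat a window with no days observed as missing, not zero.
- Summarise the rate, its change from the pre-treatment rate, and days observed. Neither document currently plans the change, but it follows from the protocol's defined baseline frequency.
- Replace the whole-study row with an on-treatment row that excludes pre-treatment seizures.
- Keep raw counts in the listing, with days observed alongside.

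In SAP 5.7, add the pre-treatment rate as the baseline seizure frequency that protocol 8.5 requires.

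The cost is SAP wording and a few lines of programming on consent, first-dose, event-start and end-of-study dates. No study procedure changes. The drawback is noise: a short screening period gives an imprecise baseline rate, and a last window of a few days gives an unstable one. Days observed must therefore be shown next to every rate.
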